5.2 COLLECTION OF SPECIMENS

5.2.1 Blood Samples

6 (10ML) Green Top Sodium Heparin Tubes for PBMC; 2 (8ML) SST Tubes for serum will be collected at the timepoints indicated in [APPENDIX C](#).

5.2.2 Handling and Processing of Specimens

The samples will be processed/stored through:

Clinical Services Program
NCI Frederick Cancer Research and Development Center
[REDACTED]

On days samples are drawn, [REDACTED] at CSP should be notified [REDACTED]
[REDACTED] She will arrange same-day courier delivery of the specimens.

5.2.3 Stool (optional)

Stool specimens will be collected from willing participants during the surveillance period, after 3-4 months on treatment and after completion of 7 months of treatment. In some instances, subjects may be asked to ship collected stool specimens to the research team at NIH. In those instances, participants will be given instructions for home self-sampling of stool ([APPENDIX F](#) and [APPENDIX G](#)) as well as instructions to ship the specimen ([APPENDIX H](#)). Samples will be stored for future studies, including whole genome shotgun sequencing of host and/or microbial DNA.

Participants will receive a cooler for transporting to clinic and/ or shipping materials which include: one brown top container and one purple top container for specimen collection, a white cardboard box with shipping materials, two biohazard plastic bags and a return label. Participants will be instructed to write the date and time of the collection on both tubes. Participants will be

instructed to freeze the specimens for at least 4 hours prior to transporting/ shipping and to ship the samples back as soon as they can after freezing so that the research staff can process the samples. The sample will be shipped to the Blood Processing Core (BPC; [name] lab) prior to transfer of coded samples for analysis to:

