1.1.3 Exploratory Objective

- Immune changes after treatment with 2 vaccines for 4 months
- Correlate changes in PET images to changes in PSA over time
- Evaluate changes in the microbiome of the gastrointestinal tract and correlate to changes in treatment, PSA and immune cell subpopulations
- Evaluate the decline in PSA in participants who received vaccine as well as MSB0011359B prior to its being discontinued.

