2.3.1 Treatment Assignment Procedures (for registration purposes only)

Cohorts

Number	Name	Description
1	Lead-In Cohort (closed December 2018)	Participants with advanced castration resistant prostate cancer (first six participants)
2	Biochemical Recurrence Cohort	Participants with biochemically recurrent prostate cancer

Arms

Number	Name	Description
1	Combination therapy (closed December 2018)	Prostvac + CV301 + MSB0011359C
2	Combination therapy + surveillance (closed)	Surveillance followed by Prostvac + CV301 then Prostvac + CV301 + MSB0011359C
3	Combination vaccine therapy +/- surveillance	Surveillance as needed followed by Prostvac + CV301

Arm Assignment

Participants in cohort 1 will be directly assigned to Arm 1 of the study. This cohort has been closed as of December 2018.

Participants in cohort 2 will be directly assigned to Arm 2, or Arm 3 of the study based upon time of enrollment. Participants enrolling after approval of amendment dated 7/29/2021 are assigned to Arm 3.

Please note: As of December 21, 2018, the 6 participants in the lead in cohort have completed the 6-week toxicity assessment period and no SAEs were seen. Per the protocol design participants will now be enrolled to the BCR cohort. The toxicity assessment of participants in the lead-in cohort is described in section [1.2.13](#).

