begin C1D1 with vaccine therapy. In this case, the 3 PSA values obtained prior to enrollment will be evaluated as if they were collected during the surveillance period while enrolled and will factor into the determination of the intra-study apex value (See Section 6.3.2) highest PSA that is within 10% of another peak PSA for the participant on-study. Any other peak PSA values that are beyond 10% of other PSA values on the study will be determined as potential lab variability and excluded from response assessment.

- With Amendment v05/10/2023, participants that have at least 3 PSA measurements in the surveillance period, with at least one of them sufficient to provide the doubling time from baseline, will not undergo any further PSA measurements in the surveillance period.

Prostvac will be administered nearly identical to the Phase III dosing with Prostvac-V given day 1 (week 1) followed by Prostvac-F on weeks 3 and 5 then monthly for an additional 5 months. Therefore, Prostvac-V is given one time (priming vaccine) followed by 7 doses of Prostvac-F (booster vaccine). The administration schema for CV301 is representative of the Phase I dose escalation trial. MVA-BN-CV301 (priming vaccine) is administered on day 1 (week 1) and week 3 followed by FPV-CV301 (booster vaccine) administered on week 5 then monthly for an additional 5 months.

MSB0011359C (anti-PDL1 TGF β Trap) will be administered at the recommended phase II dose of 1200mg by IV infusion every 2 weeks for 3 months (6 doses) starting after 4 months of concurrent Prostvac and CV301.

Effective with amendment v7/29/2021, MSB0011359C will no longer be given as part of the treatment combination for the Biochemical Recurrence cohort (Arms 2 and 3). This cohort will now receive Prostvac and CV301 during months 1-7 following surveillance.

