4.2.2 Antibiotics

Antibiotics will be delivered as required. Co-administration of protocol treatments can be done at the discretion of the investigator. Prophylactic antibiotics (e.g., prevention of urinary tract infections) may be allowed at the discretion of the investigator.

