¹⁵ For participants in the BCR cohort, two NaF PET Scans will be done when logistically feasible. These scans are for research purposes only. These scans will not be used to evaluate for clinical progression of disease.

¹⁶ Can be done any time prior to first treatment.

¹⁷ Surveys are optional at all time points and can be done as noted on study calendar, and every 3 months thereafter while participants are on-study. If surveys are not done, reason will be documented.

¹⁸ Participants will be asked to give stool samples during the surveillance period, after 3-4 months on treatment and after completion of 7 months of treatment (Section **5.2.3**). Note: These are optional.

¹⁹ When logistically feasible, PSMA PET scans should be done in the first two months during surveillance (or within 4 months of treatment initiation if surveillance period is shorter per Amendment v05/10/2023 and within 8 weeks after completing treatment. If PSMA PET is obtained within 8 weeks of starting surveillance, it will not need to be repeated during the surveillance period.

²⁰ With Amendment v05/10/2023, participants that have at least 3 PSA measurements in the surveillance period, with at least one of them sufficient to provide the doubling time from baseline, will not undergo any further PSA measurements in the surveillance period.

²¹ Participants starting treatment per Amendment v05/10/2023 with a surveillance period of 8 weeks or shorter do not need to repeat CT and Tc99 imaging on C1D1

Abbreviated Title: Combination Immunotherapy

Version Date: 05/10/2023

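### A man whose qualifying PSA values all precede enrollment can start vaccines with no scheduled baseline stool sample

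*Combined protocol and SAP*

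**What the plan says.** The exploratory objective in section 1.1.3 is: "Evaluate changes in the microbiome of the gastrointestinal tract and correlate to changes in treatment, PSA and immune cell subpopulations". Section 5.2.3 gives the sampling times: "Stool specimens will be collected from willing participants during the surveillance period, after 3-4 months on treatment", with a last sample once the 7 months of treatment are complete. Footnote 18 of the biochemical recurrence calendar (section 18.1) repeats them, beginning "Participants will be asked to give stool samples during the surveillance period, after 3-4 months on treatment", and notes that the samples are optional. In the calendar grid, the first stool mark also falls under surveillance.

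Several places deal with the length of surveillance:

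- Section 2.3.1 describes Arm 3 as "Surveillance as needed followed by Prostvac + CV301".
- The précis says that participants may have a surveillance period and are treated after it where it applies.
- Section 3.1 lets men already monitored at NIH enroll partway through. It treats their earlier PSA values as if they had been collected in surveillance on study.
- Under Amendment v05/10/2023 (section 3.1 and calendar footnote 20), men with at least three surveillance PSA values, at least one of them sufficient for the doubling time, "will not undergo any further PSA measurements in the surveillance period".

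Baseline research blood is handled differently. Footnote 16 says of it: "Can be done any time prior to first treatment".

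**The concern.** The first stool sample is tied to a period that can now be very short or may not occur on study at all. A treatment-related change in the microbiome needs a sample from before the first vaccine, and one that is missed cannot be obtained later. A man without it can contribute nothing to an analysis of change from a pre-treatment baseline, or to its correlation with PSA or immune cells. The sponsor adapted other assessments to shorter surveillance, so the stool schedule looks like an oversight rather than a choice.

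**Working it through.** The documents give no sample size, test or rate for the microbiome objective, so there is no stated figure to reproduce. The check compares the schedule provisions.

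**Step 1: is there another pre-vaccine stool point?** Section 5.2.3 and footnote 18 list the same three times: surveillance, 3-4 months on treatment, and after 7 months. The baseline evaluation in section 2.4 does not include stool. The answer is no.

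**Step 2: can on-study surveillance be absent?** Section 3.1 gives its own example. A man has three monthly PSA values before enrollment, enrolls, has a fourth value one month later, and then starts C1D1.

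- On the four-value schedule: 4 − 3 = 1 value still to be taken on study. The month leading up to it is a surveillance period in which stool can be collected.
- Under the amendment, if at least one of the three values is sufficient for the doubling time: 3 − 3 = 0 values still to be taken. Nothing in the schedule then holds him in surveillance before C1D1.

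The second line is an inference. It combines the counting rule in section 3.1 with the amendment and with the descriptions of surveillance in the précis and section 2.3.1. No sentence says that such a man goes directly to treatment, but the provisions allow it.

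**Step 3: what is lost?** Three samples give three within-man comparisons: baseline to month 3-4, baseline to month 7, and month 3-4 to month 7. Without the baseline sample, only the last remains. Both of its samples are on treatment, so it cannot show what changed from the pre-vaccine state.

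**Step 4: how are other assessments treated?**

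| Assessment (section 18.1) | Timing provision | Allows for short surveillance? |
|---|---|---|
| PSMA PET, footnote 19 | Early surveillance, or within 4 months of starting treatment if surveillance is shorter | Yes |
| CT and Tc99, footnote 21 | No repeat at C1D1 if surveillance was 8 weeks or shorter | Yes |
| Research blood, footnote 16 | Any time before first treatment | Yes |
| Stool, footnote 18 | Surveillance period only | No |

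**Step 5: how many men?** This is not given and cannot be derived. The range runs from none to all 25 evaluable Arm 3 men. Neither extreme is likely, and the documents do not narrow it.

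**The case against.** The strongest reply is that the amendment stops PSA draws and does not abolish surveillance. Footnotes 19 and 21 speak of a shorter period, and section 3.1 still says that Cohort 2 has four monthly checks. A man with a short on-study surveillance period can give his sample within it. Even a man with none is enrolled before C1D1. Section 5.2.3 already provides home collection and shipping, and nothing forbids a sample in that gap.

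The number of men may also be small. Arm 3 opened with the amendment of 7/29/2021, just over 21 months before the surveillance change. At the anticipated 1 to 2 men per month (section 10.2), 21 to 42 men could have enrolled by then, against a target of 25. Finally, stool is optional, the objective is exploratory, the samples are stored for future studies, and section 10.4.9 names no microbiome analysis.

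Most of this stands as a limit on the size of the point. It does not close the gap. That a sample is not forbidden does not mean that it is scheduled, and nothing prompts staff to request one before C1D1. The accrual argument uses the anticipated rate, since actual accrual is not given. Footnote 21 provides for men starting treatment under the amendment, so the sponsor expected some.

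A reader might go further and infer that every man with three earlier PSA values skips surveillance. The documents do not support that. One value must be sufficient for the doubling time, and the earlier monitoring must have been at NIH and consistent with the study calendar. A reader might also infer that microbiome change cannot be calculated for these men. That too is unsupported, because the month 3-4 to month 7 change survives and an unscheduled baseline sample remains possible.

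**Conclusion.** The point holds in a limited form. As written, the schedule gives no pre-vaccine stool sample to a man whose qualifying PSA values all precede enrollment and who therefore has no surveillance on study. His change from a pre-treatment baseline is lost unless staff collect a sample outside the schedule. The conclusion assumes that values from before enrollment count toward the amendment's three, which section 3.1 indicates but the amendment text does not repeat.

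The effect is confined to an optional, exploratory endpoint; no primary, secondary or safety conclusion depends on it. A reader might want to express the loss as reduced power. The documents give no planned microbiome test, effect size or number of affected men, so any such figure would rest wholly on assumption. Nor do they show that the affected men differ from the rest: section 2.1.5 names current NIH patients as the recruitment source for the whole trial.

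**What to change.** In section 5.2.3 and calendar footnote 18, change the first stool time point from the surveillance period to any time after consent and before the first vaccine, following footnote 16 for research blood. The other two time points stay as they are.

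The cost is one sentence and one footnote, which could go into the next amendment. No sample is added, and the home collection procedure is already in place. The downside is that the interval from baseline sample to first vaccine will vary between men. Section 5.2.3 already has participants write the collection date and time on the tubes, so that interval can be reported with the results. The change cannot recover a baseline for men already vaccinated without one.

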5.2.4 Imaging Evaluations

An exploratory objective has been added to evaluate possible changes in PET images over time as they relate to PSA (i.e., NaF PET) (Section [3.4.1](#)). The procedures for performing the NaF PET will follow clinical policies, no special procedures apply to this additional assessment for research purposes.

5.2.5 Questionnaires (OPTIONAL)

5.2.5.1 Evaluating Quality of Life in the BCR Population

Little has been formally evaluated about the impact of PSA kinetics on participants with BCR. Beginning with amendment A, participants enrolled in the BCR cohort will be asked to complete a prostate cancer specific QOL survey with 18 questions (MAX-PC) as well as the FACT-P survey at the following time points: Baseline, start of vaccines, at month 4 and month 7 and approximately every 3 months thereafter.

Each survey will take approximately 5 minutes to complete and they will be administered in English. The surveys being used have been published and vetted as appropriate QOL tools [44-46].

5.3 SAMPLE STORAGE, TRACKING, AND DISPOSITION

5.3.1 Blood Samples/Immunologic Assays

Samples will be ordered in CRIS and tracked through Clinical Trial Data management system. Should a CRIS screen not be available, CRIS downtime procedures will be followed. Samples will not be sent outside NIH without appropriate approvals and/or agreements, if required. Any transfer of materials to other NIH or non-NIH investigators will occur following NIH Intramural Research Program guidelines. If the subject withdraws consent the participant's data will be excluded from future distributions, but data that have already been distributed for approved research use will not be able to be retrieved.

All data associated with the participant samples is protected by using a secure database. All samples drawn at the NIH Clinical Center will be transported to the NCI Frederick Central Repository by couriers.

Samples will be tracked and managed by Central Repository database. All samples will be stored in either a -20°C or -80°C freezer. These freezers are located at NCI Frederick Central Repository in Frederick, Maryland.

A subcontractor manages the NCI Frederick Central Repositories under subcontract to Leidos Biomedical Research, Inc. NCI Frederick Central Repositories store, among other things,

biological specimens in support of NIH clinical studies. All specimens are stored in secure, limited-access facilities with sufficient security, backup, and emergency support capability and monitoring to ensure long-term integrity of the specimens for research.

The subcontractor's role is limited to clinical research databases and repositories containing participant specimens. It does not conduct or have any vested interest in research on human subjects, but does provide services and support the efforts of its customers, many of which are involved in research on human subjects.

The NCI Frederick Central Repository will accept only coded, linked samples and sample information. Protected information will not be sent electronically or by hard copy or on vial labels.

Sample data is stored in the BioSpecimen Inventory System II (BSI). This inventory tracking system is used to manage the storage and retrieval of specimens, as well as to maintain specimen data. BSI is designed for controlled, concurrent access. It provides a real-time, multi-user environment for tracking millions of specimens. The system controls how and in what order database updates and searches are performed. This control prevents deadlocks and race conditions. For security, BSI has user password access, 3 types of user access levels, and 36 user permissions (levels of access) that can be set to control access to the system functions. BSI provides audit tracking for processes that are done to specimens including shipping, returning to inventory, aliquoting, thawing, additives, and other processes. BSI tracks the ancestry of specimens as they are aliquoted, as well as discrepancies and discrepancy resolution for specimens received by the repository. If a specimen goes out of the inventory, the system maintains data associated with the withdraw request. Vials are labeled with a unique BSI ID which is printed in both eye-readable and bar-coded format. No participant-specific information is encoded in this ID.

Investigators are granted view, input, and withdraw authority only for their specimens. They may not view specimen data or access specimens for which they have not been authorized. Access to specimen storage is confined to repository staff. Visitors to the repositories are escorted by repository staff at all times.

Samples will be used for research analysis, including immunologic monitoring as outlined in Section 5.1. All specimens for analysis will be requested from Leidos Biomedical, Inc. and will be delivered by Leidos Biomedical, Inc. couriers to the Laboratory of Tumor Immunology and Biology.

5.3.2 Stool Samples (Blood Processing Core/[name] Laboratory)

All samples sent to the Blood Processing Core (BPC) will be barcoded, with data entered and stored in the Labmatrix utilized by the BPC. This is a secure program, with access to Labmatrix limited to defined [name] lab personnel, who are issued individual user accounts. Installation of Labmatrix is limited to computers specified by [name]. These computers all have a password restricted login screen.

Labmatrix creates a unique barcode ID for every sample and sample box, which cannot be traced back to participants without Labmatrix access. The data recorded for each sample includes the participant ID, name, trial name/protocol number, time drawn, cycle time point, dose, material type, as well as box and freezer location. Participant demographics associated with the clinical center participant number are provided in the system. For each sample, there are notes associated with the processing method (delay in sample processing, storage conditions on the ward, etc.).

Barcoded samples are stored in barcoded boxes in a locked freezer at either -20 or -80°C according to stability requirements. These freezers are located onsite in the BPC and offsite at NCI Frederick Central Repository Services in Frederick, MD. Visitors to the laboratory are required to be accompanied by laboratory staff at all times.

Access to stored clinical samples is restricted. Samples will be stored until requested by a researcher named on the protocol. All requests are monitored and tracked in Labmatrix. All researchers are required to sign a form stating that the samples are only to be used for research purposes associated with this trial (as per the IRB approved protocol) and that any unused samples must be returned to the BPC. It is the responsibility of the NCI Principal Investigator to ensure that the samples requested are being used in a manner consistent with IRB approval.

Following completion of this study, samples will remain in storage as detailed above. Access to these samples will only be granted following IRB approval of an additional protocol, granting the rights to use the material.

If, at any time, a participant withdraws from the study and does not wish for their existing samples to be utilized, the individual must provide a written request. Following receipt of this request, the samples will be destroyed (or returned to the participant, if so requested), and reported as such to the IRB. The PI will record any loss or unanticipated destruction of samples as a deviation. Reporting will be per the requirements of section [7.2](#).

Sample barcodes are linked to participant demographics and limited clinical information. This information will only be provided to investigators listed on this protocol, via registered use of the Labmatrix. It is critical that the sample remains linked to participant information such as race, age, dates of diagnosis and death, and histological information about the tumor, in order to correlate genotype with these variables.

5.3.3 Protocol Completion/Sample Destruction

Once primary research objectives for the protocol are achieved, intramural researchers can request access to remaining samples, provided they have an IRB-approved protocol and participant consent.

Samples and associated data will be stored permanently unless the participant withdraws consent. If the participant withdraws consent the participant's data will be excluded from future distributions, but data that have already been distributed for approved research use will not be able to be retrieved. The PI will record any loss or unanticipated destruction of samples as a deviation. Reporting will be per the requirements of section [7.2](#).

